Appendix 1 Schedule of Events

Visit number	Screening	Wash-out			Run-in		Efficacy Assessment								Safety Extension			Follow-up
	V1	V2	V3	V4	V5	V6	V7	V8	V9	V10	V11	V12	V13	V14	V15	V16	V17	V18
Time to Randomization Visit (wk)	-11	-8	-6	-2	-0.5	0	2	4	6	12	24	36	48	60	72	84	96	98
Off-site phone visit			X													X		
Informed Consent	X																	
EQ-5D-3L						X					X			X			X	
Screening for I/E criteria	X	X			X													
Demographics and medical history	X																	
Diet & exercise counseling		X		X														
Physical exam					X									X				X
Abbreviated physical exam	X								X		X	X	X		X		X	
Record height	X																	
Record body weight	X				X				X	X	X	X	X	X	X		X	X
Dispense diary & glucometer		X		X														
Diary & glucometer record review			X	X	X	X	X	X	X	X	X	X	X	X	X	X	X	X
Start wash-out		X																
Dispense Run-in Medication				X														
Randomization						X												
Vital signs	X			X	X		X	X	X	X	X	X	X	X	X		X	X
ECG	X				X						X			X			X	
Discontinue non-metformin OHA		X																
Dispense bexagliflozin						X				X	X	X	X	X	X			
Dispense glimepiride						X	X	X	X	X	X	X	X	X	X			
Blood draw for clinical lab test	X				X				X	X	X	X	X	X	X		X	X
Urine collection	X				X				X	X	X	X	X	X	X		X	X
AE		X	X	X	X	X	X	X	X	X	X	X	X	X	X	X	X	X
Con Med		X	X	X	X	X	X	X	X	X	X	X	X	X	X	X	X	X

Appendix 2 Schedule of Clinical Laboratory Tests

	Screening	Wash-out		Run-in		Efficacy Assessment								Safety Extension			Follow-up	
Visit Number	V1	V2	V3	V4	V5	V6	V7	V8	V9	V10	V11	V12	V13	V14	V15	V16	V17	V18
Time to Randomization Visit (weeks)	-11	-8	-6	-2	-0.5	0	2	4	6	12	24	36	48	60	72	84	96	98
Hematology	X				X				X		X		X	X			X	X
Serum chemistry electrolytes	X				X				X		X		X	X			X	X
Fasting Plasma Glucose	X				X				X	X	X	X	X	X	X		X	X
HbA1c	X				X					X	X	X	X	X	X		X	X
Lipids	X				X						X			X			X	X
Urinalysis	X				X				X	X	X	X	X	X	X		X	X
Urine pregnancy test (UPT)	X				X				X	X	X	X	X	X	X		X	X

[figure not shown]

1. GLOSSARY OF ABBREVIATIONS

Abbreviation	Description
ADA	American Diabetes Association
AE	Adverse Event
ANCOVA	Analysis of Covariance
ATC	Anatomical Therapeutic Chemical
BMI	Body Mass index
CEC	Cardiovascular Endpoint Committee
CI	Confidence Interval
CRF	Case Report Form
CTCAE	Common Terminology Criteria for Adverse Events
CV	Coefficient of Variation
dL	Deciliter
DSMB	Data and Safety Monitoring Board
ECG	Electrocardiogram
eGFR	Estimating Glomerular Filtration Rate
FPG	Fasting Plasma Glucose
GLP-1	Glucagon-like Peptide-1
GMI	Genital Mycotic Infection
GGT	Gamma Glutamyl Transferase
HbA1c	Hemoglobin A1c
HBsAg	Hepatitis B Surface Antigen
HCV	Hepatitis C Virus
Hct	Hematocrit
HDL-C	High Density Lipoprotein Cholesterol
Hgb	Hemoglobin
HIV	human immunodeficiency virus
ICH	International Conference on Harmonization

Abbreviation	Description
ITT	Intention to Treat
IVRS	Interactive Voice Randomization System
IWRS	Interactive Web Randomization System
LDL-C	Low Density Lipoprotein Cholesterol
LOCF	Last Observation Carried Forward
MACE	Major Adverse Cardiovascular Event
Max	Maximum
MCH	Mean Cell Hemoglobin
MCHC	Mean Cell Hematocrit
MCV	Mean Cell Volume
MDRD	Modification of Diet in Renal Disease
MedDRA	Medical Dictionary for Regulatory Activities
Mg	Milligram
MI	Myocardial Infarction
Min	Minimum
mL	Milliliter
MMRM	Mixed Model Repeated Measures
MODY	Maturity-onset Diabetes of the Young
N/A	Not Applicable
NA	Not Applicable
Na	Sodium
NCI	National Cancer Institute
OHA	Oral Hypoglycemic Agent
PP	Per Protocol
PR	Time from the beginning of the P wave to the beginning of the QRS complex in electrocardiogram
PT	Preferred Term
QRS	Graphical deflections corresponding to ventricular depolarization in a typical electrocardiogram

Abbreviation	Description
QTc	Time between the start of the Q wave and the end of the T wave in the ECG, corrected for heart rate
RBC	Red Blood Cell
RR	Time between the start of one R wave and the start of the next R wave in the ECG
SAE	Serious Adverse Event
SAP	Statistical Analysis Plan
SBP	Systolic Blood Pressure
SD	Standard Deviation
SE	Standard Error
SGLT2	Sodium Glucose Linked Transporter 2
SI	Standard International System of Units
SMBG	Self-Monitored Blood Glucose
SOC	System Organ Class
SOP	Standard Operating Procedure
SS	Safety Set
T2DM	Type 2 Diabetes Mellitus
TC	Total Cholesterol
TEAE	Treatment Emergent Adverse Event
TG	Triglycerides
TLF	Table, Listing And Figure
TZD	Thiazolidinedione
UACR	Urine Albumin To Creatinine Ratio
UGE	Urine Glucose Excretion
ULN	Upper Limit of Normal
UPT	Urine Pregnancy Test
UTI	Urinary Tract Infection
WBC	White Blood Cell
WHO-DD	World Health Organization Drug Dictionary

2. PURPOSE

The purpose of this statistical analysis plan (SAP) is to ensure that the data listings, summary tables and figures which will be produced, and the statistical methodologies that will be used, are complete and appropriate to allow valid conclusions regarding the study objectives.

2.1. RESPONSIBILITIES

Theracos has designed the study protocol and is responsible for the conduct of the study. INC Research is responsible for the development and validation of a clinical database using MediData RAVE platform.

INC Research will perform the statistical analyses and are responsible for the production and quality control of all tables, figures and listings.

Adverse events that have met the seriousness criteria defined in the protocol are reported on the serious adverse event (SAE) forms using MediData RAVE platform. An SAE case, consists of the information reported in the SAE forms, subject characteristics documented in the case report forms (CRF), and additional source data such as a hospital discharge summary, is recorded in a validated ARGUS database which is managed by Covance. Any discrepancies in critical data fields of each SAE will be reconciled between the ARGUS and THR-1442-C-480 clinical database prior to database lock. The SAE coding, analyses and summaries are based on the final study data recorded in the clinical database. Detailed serious adverse event follow-up data will be reported from ARGUS database and not included this report.

Theracos will perform review of all tables, figures and listings before the finalization.

2.2. TIMINGS OF ANALYSES

The final analysis of safety and efficacy is planned after all subjects have completed the 96 weeks of treatment period and a two-week post-dose follow-up period. The treatment assignment is blinded to all study personnel throughout the 96-week treatment and the two-week follow-up periods. The database will be cleaned and locked followed by the unblinding of subject treatment codes.

3. STUDY OBJECTIVES

3.1. PRIMARY OBJECTIVE

The primary efficacy objective of this trial is to demonstrate that bexagliflozin is non-inferior to glimepiride by evaluating the treatment effect on Hemoglobin A_{1c} (HbA_{1c}) reduction at week 60 in subjects whose type 2 diabetes mellitus (T2DM) is inadequately controlled by metformin.

3.2. SECONDARY OBJECTIVES

- To evaluate the treatment effect of bexagliflozin vs. glimepiride on the change in body weight in subjects with baseline body mass index (BMI) ≥ 25 kg/m² at week 60
- To evaluate the treatment effect of bexagliflozin vs. glimepiride on the change in systolic blood pressure (SBP) in subjects with baseline SBP ≥ 140 mmHg at week 60
- To evaluate the treatment effect of bexagliflozin vs. glimepiride on the difference in proportion of subjects with ≥ 1 severe or documented symptomatic hypoglycemia events over 96 weeks
- To evaluate if bexagliflozin is superior to glimepiride on HbA_{1c} reduction at week 60

3.3. EXPLORATORY EFFICACY OBJECTIVES:

- To assess the treatment effect of bexagliflozin vs. glimepiride on the change in the proportion of subjects achieving HbA_{1c} $< 7.0\%$ over time
- To assess the treatment effect of bexagliflozin vs. glimepiride on the change in HbA_{1c} over time
- To assess the treatment effect of bexagliflozin vs. glimepiride on the change in fasting plasma glucose (FPG) over time
- To assess the treatment effect of bexagliflozin vs. glimepiride on the change in SBP over time
- To assess the treatment effect of bexagliflozin vs. glimepiride on the change in body weight over time
- To assess the treatment effect of bexagliflozin vs. glimepiride on the difference in proportion of subjects with ≥ 1 severe or documented symptomatic hypoglycemia events over time

3.4. SAFETY OBJECTIVES

- To compare the effects of bexagliflozin vs. glimepiride on the incidence of adverse events of interest. Adverse events of interest are urinary tract infections (UTI), pyelonephritis urosepsis, genital mycotic infections (GMI), diuretic effects including hypovolemia, hypotension episodes, hypoglycemia, hepatotoxicity, major adverse cardiovascular events (MACE), fractures, malignancies, hypersensitivity reactions, acid-base disorders including diabetic ketoacidosis, rash, and renal failure events
- To compare the effects of bexagliflozin vs. glimepiride on general safety assessments including treatment emergent adverse events, clinical laboratory events, 12-lead electrocardiograms (ECG) parameters, physical examinations, vital signs including orthostatic blood pressure, and use of concomitant medications

3.5. OTHER OBJECTIVES

- To compare the effects of bexagliflozin and glimepiride on health-related quality of life using a validated instrument EQ-5D-3L

3.6. BRIEF DESCRIPTION

[figure not shown]
THR-1442-C-480 is a phase 3, multi-center, randomized, double-blind, active-controlled study and aims to demonstrate that bexagliflozin is non-inferior to glimepiride as add-on therapy in subjects whose T2DM is not adequately controlled by metformin treatment. The primary efficacy endpoint is the change in HbA_{1c} from baseline at week 60. The study will enroll T2DM patients who are treated with only metformin (metformin-only) or who are treated with metformin and one additional oral hypoglycemic agent (metformin-and-oral hypoglycemic agent [OHA]).

All subjects must have taken metformin at a stable dose of ≥ 1500 mg/day for ≥ 8 weeks prior to screening. Subjects can be eligible for the metformin-only treated group if they have received < 14 days of any other antidiabetic medications in the 8 weeks prior to screening. Subjects can be eligible for the metformin-and-OHA treated group if they have received ≥ 14 days of no more than 1 other OHA in the 8 weeks prior to screening; subjects taking any other antidiabetic medication (in addition to metformin and the 1 OHA) for < 14 days in the 8 weeks prior to screening are allowed.

A total of 420 subjects who meet all the inclusion criteria, none of the exclusion criteria, and who consent to participate in the study are eligible for study enrollment. Metformin-and-OHA treated subjects will undergo a 6-week washout of the non-metformin OHA prior to the start of run-in. Subjects who complete the 2-week run-in and who meet all eligibility criteria will be randomized in a 1:1 ratio to receive

once daily double-blind treatment of either active bexagliflozin tablets with placebo glimepiride capsules (Group 1) or placebo bexagliflozin tablets and active glimepiride capsules (Group 2). Active treatment in Group 1 will be bexagliflozin tablets, 20 mg. Active treatment in Group 2 will be glimepiride capsules, 2, 4, or 6 mg. Study subjects will continue receiving open-labeled metformin background medication during the entire study at a stable dose and frequency. The treatment period will last 96 weeks and be conducted in an outpatient setting (Figure 1).

Figure 1 Study Design

3.7. SUBJECT SELECTION

The study population will include approximately 420 subjects whose T2DM is inadequately controlled by metformin and who meet all of the inclusion criteria, none of the exclusion criteria. Clinical sites in the North America and Europe are anticipated to recruit subjects. Clinical sites in other continents may also participate in the trial.

3.7.1. Inclusion Criteria

Refer to protocol Section 4.2 for a list of inclusion criteria.

3.7.2. Exclusion Criteria

Refer to protocol section 4.3 for a list of exclusion criteria.

3.8. DETERMINATION OF SAMPLE SIZE

An approximate total of 420 subjects will be randomized and equally allocated to receive:

- bexagliflozin tablets, 20 mg and glimepiride, placebo capsules (referred to as bexagliflozin group in this document)
- bexagliflozin tablets, placebo and glimepiride capsules, 2 mg, 4 mg, or 6 mg (referred to as glimepiride group in this document).

The sample size calculation for this study is based on a two group t-test with a one-sided significance at the 0.025 level and the following assumptions:

- The non-inferiority limit (margin) for mean change from baseline to week 60 in HbA_{1c} comparing bexagliflozin group to glimepiride group will be 0.35%
- The standard deviation for the change from baseline to week 60 in HbA_{1c} for bexagliflozin group and glimepiride group will be 1.0%

Under the above assumptions, an estimated sample size of 172 subjects is needed in each treatment arm to determine non-inferiority of bexagliflozin to glimepiride with respect to change in HbA_{1c} at week 60 from baseline. This estimation is based on a one-sided t-test with 90% power at a 0.025 level of significance. A sample size of 210 per arm has been selected to account for approximate 18% drop-out rate and to allow adequate safety evaluation. The total sample size for this study will be 420 subjects.

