9.2 Determination of Sample Size

Approximate total 420 subjects will be randomized and equally allocated to receive bexagliflozin tablets 20 mg or placebo, and glimepiride capsules, 2 mg, 4 mg, 6 mg or placebo.

The sample size calculation for this study is based on a two group t-test with a one-sided significance at the 0.025 level and the following assumptions:

1. The non-inferiority limit (margin) for mean change from baseline to week 60 in HbA1c comparing bexagliflozin group to glimepiride group will be 0.35%

2. The pooled standard deviation for the change from baseline to week 60 in HbA1c for bexagliflozin group and glimepiride group will be 1.0%

Under the above assumptions, an estimated sample size of 172 patients is needed in each treatment arm to detect non-inferiority of bexagliflozin to glimepiride with respect to change in HbA1c at week 60 from baseline. This estimation is based on a one-sided t-test with 90% power at a 0.025 level of significance. A sample size of 210 per arm has been selected to account for approximate 18% drop-out rate and to allow adequate safety evaluation. The total sample size for this study will be 420 subjects.

This study will be conducted at multiple investigative sites and will likely involve various numbers of subjects at each site. Enrollment will be on a competitive basis, but will be capped at 40 subjects from each site.

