8.1.1. Primary Efficacy Analysis

Let $\mu_{\text{bexagliflozin}}$ and $\mu_{\text{glimepiride}}$ represent the mean changes from baseline in HbA_{1c} at Week 60 for bexagliflozin and comparator groups, respectively. The following hypotheses will be tested:

$$H_0: \mu_{\text{bexagliflozin}} - \mu_{\text{glimepiride}} > \delta \text{ versus}$$

$$H_1: \mu_{\text{bexagliflozin}} - \mu_{\text{glimepiride}} \leq \delta$$

Non-inferiority margin δ is chosen to be 0.35% using clinical judgment, with reference to relevant regulatory guidance, and justified by published glimepiride efficacy study (Charpentier et al. 2001).

This hypothesis will be tested based on ITT analysis set. Missing data will be imputed via multiple imputations, following which the MMRM will be repeated on the complete datasets with results combined across complete datasets using standard multiple imputations techniques; HbA_{1c} values collected after the start of rescue medication will not be excluded. A pattern-mixture model will be used to explore the impact of the missing data. Imputation will be conducted within each treatment arm and subgroup (treatment completer vs. treatment terminated early) under the assumption that non-adherent subjects with missing data will follow the same trajectory of non-adherent subjects with values observed. All efforts will be made to retain subjects in the study. If treatment is discontinued, subjects are encouraged to remain in the study and complete all scheduled visits, including final follow-up visit. However, with all efforts, insufficient values may be available for reliable imputation. This analysis will be performed only if $\geq 3\%$ (approximately 6) of subjects in each treatment arm completed scheduled week 60 visit after treatment is stopped. This number is chosen to allow sufficient data to establish a regression model for imputation. For this analysis, the following three-step approach outlined below will be used:

1. Non-monotone (intermediate visits) missing data will be imputed first using the Monte Carlo Markov Chain (MCMC) method under the MAR assumption in all

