treatment arms (using the MCMC statement in PROC MI). Multiple chains option (CHAIN=MULTIPLE option in the MCMC statement of PROC MI) will be used. For the non-monotone imputation of the HbA_{1c} missing data, a multivariate normal model will be used including variables for the HbA_{1c} at baseline and all post-baseline visits within each treatment group. Five hundred imputed datasets will be generated.

2. After the non-monotone missing data have been imputed, the remaining monotone missing data will be imputed within each treatment arm and subgroup, defined by whether subject completed 60 week of study treatment, using regression approach. The predictors for the regression imputation model at any time point will be region, treatment background (metformin only or metformin and OHA), baseline eGRF (≥ 90 or < 90 ml/min/1.73 m²), and HbA_{1c} at all previous time points, including baseline. Imputations will be performed using a sequence of regression-based imputations (using PROC MI statement MONOTONE REG) at each post-baseline time point.
3. Imputed data in each of the multiple imputed datasets will be analyzed using a mixed model repeated measures (MMRM) approach. The MMRM model will include region, terms for treatment background (metformin only or metformin and OHA), baseline eGRF (≥ 90 or < 90 ml/min/1.73 m²), treatment, visit, treatment-by-visit interaction, and the baseline HbA_{1c} value, as a fixed effect covariate. The analysis will evaluate the mean change from baseline in HbA_{1c} over the 60-week double blind treatment period. An unstructured covariance will be used to model the within subject correlation. The Kenward Roger approximation will be used to estimate denominator degrees of freedom. If the model with the unstructured covariance structure does not converge, an autoregressive(1) covariance structure will be used. HbA_{1c} values obtained after the start of rescue medication will not be excluded from the analysis. The treatment and treatment by visit interaction terms allow for comparisons of the treatment groups at each visit, and over week 12 to week 60. Least squares (LS) mean treatment differences between the bexagliflozin group and the placebo group at week 60 will be estimated from the model. The LS mean results from all imputed datasets will be combined using the Rubin's combination rule (PROC MIANALYZE).

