13. CHANGE FROM ANALYSIS PLANNED IN PROTOCOL

In all analysis models, continuous HbA_{1c} at baseline is used as fixed effect, in place of randomization stratification factor of HbA_{1c} group at baseline. In all models, eGFR at baseline category is used as fixed effect, in place of randomization stratification factor of eGFR at screening.

Primary analysis of the primary endpoint was MMRM using available data in the protocol. In SAP, a “retrieved dropout” analysis is used for handling missing data is used as primary analysis if data allows. Retrieve dropouts are subjects who discontinued treatment but still had their efficacy measurements at the planned visit. Sensitivity analysis of LOCF is planned in the protocol, but removed in SAP since LOCF does not add more information on sensitivity in addition to tipping point analysis.

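### The 90% power in SAP 3.8 belongs to a t-test on 172 observed subjects per arm; no power is given for the retrieved-dropout imputation that can become primary, and with few retrieved subjects it is far lower

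*SAP*

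**What the plan says.** SAP 3.8 states that "The sample size calculation for this study is based on a two group t-test with a one-sided significance at the 0.025 level", with a margin of 0.35, an SD of 1.0 and 172 subjects per arm, and adds: "This estimation is based on a one-sided t-test with 90% power at a 0.025 level of significance". Protocol 9.2 gives the same sizing: "A sample size of 210 per arm has been selected to account for approximate 18% drop-out rate and to allow adequate safety evaluation".

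SAP 13 records a change of primary method: "Primary analysis of the primary endpoint was MMRM using available data in the protocol", whereas the SAP uses a retrieved-dropout analysis where the data permit. SAP 8.1.1 describes it: "Imputation will be conducted within each treatment arm and subgroup (treatment completer vs. treatment terminated early"). For the monotone step, "The predictors for the regression imputation model at any time point will be region, treatment background (metformin only or metformin and OHA), baseline eGRF", followed by HbA1c at baseline and at every preceding visit. There are 500 imputations, combined by Rubin's rules. The method applies only if at least 3% of each arm, put at about 6 subjects, attend week 60 after stopping treatment. Otherwise the MMRM on available data is primary. Non-inferiority is concluded if the 95% interval lies below 0.35.

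Neither document gives a power figure for the imputation analysis, or an expected number of retrieved subjects.

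**The concern.** The t-test's variance comes from 172 observed values per arm and nothing else. Under the imputation, every early stopper without a week-60 value is filled in from a regression estimated on the early stoppers in the same arm who do have one. When those donors are few, the regression is poorly determined, and Rubin's between-imputation variance carries that into the deciding interval. The sizing has no term for it.

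A truly equivalent drug could then miss the margin because of imputation noise, and under SAP 8.2 no secondary endpoint would be tested. The behaviour is also perverse. Below the 3% threshold the primary analysis is close to what was sized; a few more retrieved subjects can replace it with something much weaker.

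**Working it through.** **1. The plan's own figures.** Inputs from SAP 3.8: margin 0.35, SD 1.0, one-sided 0.025, power 90%. A true difference of 0 is not printed but is needed to reproduce 172.

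- n per arm = 2 × (1.960 + 1.282)² × 1.0² / 0.35² = 171.6, so 172.
- SE of the difference = √(2/172) = 0.108. Power = Φ(0.35/0.108 − 1.96), about 90% (noncentral t: 89.9%).
- 172 / 0.82 = 209.8, so 210. The allowance is 210 − 172 = 38 per arm.

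All three printed figures reproduce.

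**2. Size of the week-60 imputation regression.** Intercept 1, region 1 (two regions in SAP 6.5), background 1, eGFR 1, baseline HbA1c 1, and HbA1c at weeks 12, 24, 36 and 48 makes 4: nine coefficients. With r retrieved subjects in an arm, the residual degrees of freedom are ν = r − 9. The threshold is 3% × 210 = 6.3 subjects. At 6 to 9 retrieved there are no residual degrees of freedom, so the regression cannot be drawn.

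Each imputation draws a residual variance equal to the estimate times ν/χ²(ν). The mean of that multiplier is ν/(ν − 2):

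| Retrieved r | ν | Mean multiplier |
|---|---|---|
| 11 | 2 | not finite |
| 12 | 3 | 3.0 |
| 15 | 6 | 1.5 |
| 20 | 11 | 1.22 |

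This is why power changes steeply between 11 and 15. It is also why results at 11 depend on the number of imputations and must be run at the SAP's 500.

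**3. Rough guide without any regression.** Treat each arm mean as a weighted mean of completers and early stoppers, with SD 1.0: Var = pc²/nc + pd²/r. Here pc and pd are the two subgroups' shares of the arm and nc is the number of completers. The documents do not say whether the 18% counts all treatment stoppers (A) or only those missing at week 60, in addition to those retrieved (B).

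- A, r = 12: (172/210)²/172 + (38/210)²/12 = 0.00390 + 0.00273 = 0.00663. SE = √(2 × 0.00663) = 0.115. Power = Φ(0.35/0.115 − 1.96), about 86%.
- B, r = 12: (160/210)²/160 + (50/210)²/12 = 0.00363 + 0.00472 = 0.00835. SE = 0.129. Power is about 77%.

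At r = 6, 15 and 20 the same formula gives 73%, 89% and 91% under A, and 65%, 80% and 83% under B. It omits both the gain from covariates and the cost of fitting nine coefficients, so it shows only the part of the loss that comes from few donors.

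**4. Simulation of SAP 8.1.1 steps 2 and 3.** 210 per arm, true difference 0, SD of change 1.0; sequential Bayesian regression within arm and early stoppers with the SAP's predictors; 500 imputations; Rubin's rules; success if the upper 95% limit is below 0.35. There were 400 trials per setting, so Monte Carlo error is at most √(0.25/400) = 2.5 points.

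Assumptions not in the documents: visit correlation (compound symmetry 0.5 or 0.7, AR(1) 0.85 or 0.9), baseline slope 0 or −0.4, and dropout spread over visits or all just after baseline. A week-60 ANCOVA stood in for the MMRM on completed data, and no intermittent missingness was simulated.

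| Retrieved per arm | A: 38 stoppers in all, range (median) | B: 38 missing plus retrieved, range (median) |
|---|---|---|
| 11 | 2-32% (10%) | 0-18% (4%) |
| 12 | 17-73% (38%) | 7-57% (21%) |
| 15 | 66-92% (80%) | 47-80% (58%) |
| 20 | 83-95% (89%) | 70-89% (77%) |

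In separate runs, ANCOVA on the observed week-60 values of the same simulated subjects had about 88-97% power.

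**The case against.** - **The arithmetic is right.** SAP 3.8 attributes the 90% to a t-test, and no passage claims it for the imputation. This stands: the defect is a mismatch between the sized test and the primary analysis. A reader might infer that 172 or 210 is miscalculated; the documents do not support that.
- **The imputation is conditional.** SAP 13 uses it only where data permit, SAP 8.1.1 makes the 3% a necessary condition and foresees too few values for reliable imputation, and the available-data MMRM is reported as supportive in any case. This partly stands. No stricter rule than 3% is given, however, and a supportive analysis does not decide non-inferiority.
- **The percentages rest on assumptions from outside the documents.** This stands, and is why only ranges are given. A reader might infer that the trial will have very low power. That needs a retrieved count just above nine, and nothing in the documents predicts the count. Under A, the loss at 20 retrieved is small or absent in most settings.
- **The collapse is really a predictor problem.** Largely so: the guide without regression gives 77-86% at 12 retrieved, against 7-73% with nine coefficients. That supports shortening the predictor list, but it does not give the analysis as written its 90%.

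**Conclusion.** The point holds as a mismatch that should be corrected before unblinding. The printed power describes the available-data analysis with 172 evaluable subjects per arm; it does not describe the imputation that displaces that analysis once the 3% condition is met. The shortfall is severe when the number retrieved only just exceeds the nine coefficients. At 15 it is moderate on most assumptions, and at about 20 it ranges from none to 20 points (90% against 70% in the worst setting under B). Below the threshold, the fallback MMRM is close to what was sized.

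Confidence is high that the 90% does not carry over. It is only moderate for any single percentage, because visit correlation, dropout timing, the number retrieved and the meaning of the 18% all have to be assumed.

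**What to change.** 1. In SAP 3.8, say that the 90% applies to the available-data analysis with 172 evaluable per arm. Add the power of the retrieved-dropout analysis by number retrieved, simulated with the SAP's 500 imputations and with assumptions and ranges shown. A single figure per count should not be entered without them.
2. In SAP 8.1.1 step 2, for early stoppers only, limit the predictors to baseline HbA1c and the immediately preceding HbA1c value. That leaves three coefficients in place of nine; completers keep the full list. In simulation this brings power to roughly 80-93% at 11 to 15 retrieved.

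Cost: SAP wording only, before unblinding, with no extra subjects or data. The stated power becomes less favourable, and the imputation uses slightly less of each early stopper's history. The shorter list does not fully restore 90% at the lowest counts, so the power table is still needed.
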